### Procedures for monitoring subject compliance 7.7

The IMP (oral tablets) will be supplied to the subject/parent(s)/legal representative(s) at protocol specified time points according to the study schedule of assessments (Table 5-1).

The Investigator will instruct the subject/parent(s)/legal representative(s) to bring back at each visit the kits (even empty) dispensed at the previous visit and containing all the remaining tablets of study medication.

The subjects/parent(s)/legal representative must record the situation of medication compliance every time the subjects take an IMP.

Drug accountability must be done in the subject/parent(s)/legal representative(s) presence in order to obtain explanations regarding discrepancies in compliance with the dosing regimen. Drug accountability must be recorded on the Drug Accountability form.

Brivaracetam

Compliance with investigational product is defined as investigational product consumption by the subject within 80% and 120% of the prescribed dosage. If a subject is found to be persistently noncompliant (<80% or >120%), the Sponsor in conjunction with the Investigator will make a decision as to whether the subject should be withdrawn from the study. 1.ation

The number of tablets dispensed and returned must be recorded in the source documents.

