3.9.5 Time to *n*th partial seizure

The evaluation of time to n^{th} partial seizure is based on the relative day of occurrence of the n^{th} partial seizure (n=1, 5, and 10) during the Treatment Period. Only seizure DRC data from the randomization up to and including the last visit of the Treatment Period will be considered. The algorithms described in Section 3.9.2 also apply to this analysis.

The time to n^{th} seizure will be calculated as the date of the n^{th} partial seizure minus the date of randomization plus 1 day for subjects who have at least n partial seizures in the Treatment Period. Subjects with fewer than n partial seizures during this period will be addressed as follows:

- Subjects who complete the Treatment Period will be analyzed as censored cases with date of censoring (ie, analyzed as non-events) based on the date of last dose of IMP during the Treatment Period.
- Subjects who discontinue due to lack of efficacy during the Treatment Period will be analyzed as having the nth seizure (i.e. as an event) on the date of last dose of IMP during the Treatment Period.
- Subjects who discontinue for reasons other than lack of efficacy during the Treatment Period will be analyzed as censored cases with date of censoring based on the date of last dose of IMP during the Treatment Period.

For those cases, time to censoring or time to event will be calculated as the date of last dose of IMP during the Treatment Period minus the date of randomization plus 1 day.

3.9.6

Dose mapping for total daily BRV dose

During the Treatment Period, subjects are to take 3 tablets twice per day (morning and evening) except for the first day where they will only take the evening dose, and the last day where they will only take the morning dose.

The 3 tablets will consist of: 2×50 mg BRV tablets and 1×25 mg PBO tablet for subjects randomized to the BRV 200mg treatment group; 1 × 25mg BRV tablet and 2 × 50mg PBO tablets for subjects randomized to the BRV 50mg treatment group; 2×50 mg PBO tablets and 1 × 25mg PBO tablet for subjects randomized to the PBO group, as shown in Table 3.1.

Table 3.1: Doses of individual BRV and PBO tablets during the Treatment Period

| | | Individua | l tablet co | ntents and | dose (mg) | |
|-----------------|--------|-----------|-------------|------------|-----------|--------|
| Treatment group | | Morning | | | Evening | |
| BRV 200mg/day | BRV 50 | BRV 50 | PBO 25 | BRV 50 | BRV 50 | PBO 25 |

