| BRV 50mg/day | PBO 50 | PBO 50 | BRV 25 | PBO 50 | PBO 50 | BRV 25 |
| РВО | PBO 50 | PBO 50 | PBO 25 | PBO 50 | PBO 50 | PBO 25 |

During the Transition Period subjects are to take 2 tablets twice per day (morning and evening) except for the first day where they will only take the evening dose, and the last day where they will only take the morning dose. The 2 tablets will consist of: 1×50 mg BRV tablet and $1 \times$ 25mg BRV tablet for subjects randomized to the BRV 200mg treatment group; 1×25 mg BRV tablet and 1×50 mg PBO tablet for subjects randomized to the BRV 50 mg treatment group; 1×10^{-10} 50mg PBO tablet and 1×25 mg PBO tablet for subjects randomized to the PBO group, as shown in Table 3.2.

Table 3.2: Doses of individual BRV and PBO tablets during the Transition Period

| | Individua | l tablet co | ntents and | dose (mg) |
|-----------------|-----------|-------------|------------|-----------|
| Treatment group | Mor | ning | Eve | ning |
| BRV 200mg/day | BRV 50 | BRV 25 | BRV 50 | BRV 25 |
| BRV 50mg/day | PBO 50 | BRV 25 | PBO 50 | BRV 25 |
| РВО | PBO 50 | PBO 25 | PBO 50 | PBO 25 |

During the Down-Titration Period in weeks 1 to 3 subjects are to take 2 tablets twice per day (morning and evening) except for the first day where they will only take the evening dose, and the last day where they will only take the morning dose. In week 4 subjects will take 2 tablets in the morning only. The total dose of BRV will decrease each week, as shown in Table 3.3.

| RV and PBO tablets during the Down-Titration |
|--|
| |

| n, | | Individual tablet contents and dose (mg) | | | | |
|-----------------|------------------------|--|--------|---------|--------|--|
| Treatment group | | Morning | | Evening | | |
| 0 | BRV 200mg/day | | | | | |
| x his | BRV 150mg/day (Week1) | BRV 50 | BRV 25 | BRV 50 | BRV 25 | |
| \sim | BRV 100mg/day (Week 2) | BRV 50 | PBO 25 | BRV 50 | PBO 25 | |
| | BRV 50mg/day (Week 3) | PBO 50 | BRV 25 | PBO 50 | BRV 25 | |
| | BRV 25mg/day (Week4) | PBO 50 | BRV 25 | - | - | |

| | Individual tablet contents and dose (mg) | | | |
|----------------------|--|--------|--------|--------|
| Treatment group | Mor | ning | Eve | ning |
| BRV 50mg/day | | | | |
| BRV 25mg/day (Week1) | PBO 50 | BRV 25 | PBO 50 | PBO 25 |
| PBO (Week 2 & 3) | PBO 50 | PBO 25 | PBO 50 | PBO 25 |
| PBO (Week 4) | PBO 50 | PBO 25 | | _ |
| РВО | | | | |
| PBO (Week 1, 2 & 3) | PBO 50 | BRV 25 | PBO 50 | PBO 25 |
| PBO (Week 4) | PBO 50 | PBO 25 | | 0 |

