7 MEASUREMENTS OF TREATMENT COMPLIANCE

IMP compliance (%) will be calculated according to the definition shown in the formula below;

Compliance(%) =
$$100 \times \frac{\text{Number of tablets taken}}{\text{Number of tablets that should have been taken}}$$

In general, for a duration where the number of tablets which should be taken per day is constant, the compliance is represented as follows;

Compliance(%) =
$$100 \times \frac{(\text{Number of tablets dispensed}) - (\text{Number of tablets returned})}{(\text{Number of tablets per day}) \times (\text{Number of days in the duration})}$$

If a period where the number of tablets which should be taken per day may not be constant, the compliance will be calculated as a weighted sum of compliance of each duration weighted by length of the duration.

Compliance(%) =
$$100 \times \sum_{i} (C_i \times W_i)$$
,

where *i* represents a duration with a constant number of tablets per day,

(Number of tablets dispensed for *i*)-(Number of tablets returned for *i*)

$$C_i = \frac{1}{(\text{Number of tablets per day for } i) \times [(\text{End date of } i) - (\text{Start date of } i)]'}$$

$$W_i = \frac{(\text{End date of } i) - (\text{Start date of } i)}{(\text{End date of Period}) - (\text{Start date of Period})^2}$$

Note that the first and last day of treatment are considered as half days because the start day of each duration will contribute evening only and the last day of it will contribute morning only.

For a period where treatment is double-blind, the number of tablets which should been taken per day is defined in Table 3.1, Table 3.2 and Table 3.3.

For instance, total planned tablet number during the Treatment Period will be calculated as 6 times the number of days from the first dose of IMP (Visit 3) up to the last visit in the period (EDV for early discontinuers, Visit 7 otherwise).

Brivaracetam

Compliance for Treatment Period (%)

$$= 100 \times \frac{(\text{Number of tablets dispensed}) - (\text{Number of tablets returned})}{6 \times [(\text{Date of EDV or Visit 7}) - (\text{Date of Visit 3})]}$$

orization For the overall compliance which consists of the Treatment Period and either the Transition Period or the Down-Titration Period, the denominator of the formula for W_i is represented as [(the latest date of EDV, Visit 7 and Visit 8) – (Date of Visit 3)].

For the Open-Label Temporary Period,
$$C_i$$
 can be applied for the above formula as only BRV
25mg tablet will be used.

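### Overall and Down-Titration compliance are weighted by calendar days, so they do not in general equal the SAP's own definition of tablets taken over tablets due

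*SAP*

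**What the plan says.** SAP section 7 opens with a ratio of totals: tablets taken over the "Number of tablets that should have been taken", times 100. For a stretch with a fixed number of tablets per day this becomes dispensed minus returned, divided by tablets per day times days.

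Where the daily number may change, the section says that "compliance will be calculated as a weighted sum of compliance of each duration weighted by" the length of that duration. It writes this as 100 × Σ(C_i × W_i), where i "represents a duration with a constant number of tablets per day" and W_i is the calendar length of i over the calendar length of the whole period. The rule carries over to the combined figure: "For the overall compliance which consists of the Treatment Period and either the Transition" or Down-Titration Period, the denominator of W_i runs in calendar days from Visit 3 to the latest of EDV, Visit 7 and Visit 8.

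SAP section 3.9.6 gives the daily tablet numbers:
- Treatment: "During the Treatment Period, subjects are to take 3 tablets twice per day (morning and evening"), which is 6 a day.
- Transition: "During the Transition Period subjects are to take 2 tablets twice per day (morning and evening"), which is 4 a day.
- Down-Titration: "During the Down-Titration Period in weeks 1 to 3 subjects are to take 2 tablets twice per day", which is 4 a day. Week 4 has 2 tablets in the morning only.

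Compliance is then summarised on the Safety Set for each period and overall, with counts in the classes below 80%, 80% to 120% and above 120%. It is also listed by subject and period. Protocol section 7.7 uses the same limits, defining compliance as "consumption by the subject within 80% and 120% of the prescribed dosage".

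**The concern.** A ratio of totals equals a weighted mean of component ratios when each weight is that component's share of the total denominator. Here the denominator is tablets due, so the matching weights are shares of tablets due. Calendar-day weights coincide with these only when the daily tablet number is constant. It is not constant across the combined periods, nor within Down-Titration.

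The SAP presents the weighted sum as the way to calculate the quantity it has just defined, not as a different measure, and gives no reason for weighting by days. The day weights give the low-tablet durations more influence than their share of the tablets.

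At stake are the overall and Down-Titration compliance figures and the class counts built on them.

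**Working it through.** The documents state no compliance result, so there is no figure to reproduce.

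**Inputs.** Tablets per day are 6, 4, 4 and 2, as above (SAP 3.9.6). Period lengths are Treatment 12 weeks = 84 days, Transition 2 weeks = 14 days and Down-Titration 4 weeks = 28 days (Protocol 5.1, SAP 2.3.1). All compliance values below are assumptions chosen to show a range.

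**Formulas.** With t_i tablets per day, d_i days and C_i compliance in duration i:
- SAP rule: A = Σ(C_i d_i) / Σ d_i
- SAP definition: B = Σ(C_i t_i d_i) / Σ(t_i d_i)

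**Where they agree.** For Treatment alone (constant 6 a day), 78% gives 78% both ways. With 78% in every duration, A and B are again both 78%. For a gap, both t_i and C_i must differ between durations.

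**Tablets due.** Treatment 84 × 6 = 504. Transition 14 × 4 = 56. Down-Titration 21 × 4 + 7 × 2 = 98.

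| Combination | Weights by days | Weights by tablets due |
|---|---|---|
| Treatment / Down-Titration | 84/112 = 75%, 28/112 = 25% | 504/602 = 83.7%, 98/602 = 16.3% |
| Treatment / Transition | 84/98 = 85.7%, 14/98 = 14.3% | 504/560 = 90%, 56/560 = 10% |

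**Worked example.** Take 75% in Treatment (378 of 504) and 100% in Down-Titration (98 of 98). A = 0.75 × 0.75 + 0.25 × 1 = 81.25%. B = (378 + 98)/602 = 476/602 = 79.1%.

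**Other assumed values.**

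| Assumed compliance | A (SAP rule) | B (definition) |
|---|---|---|
| Treatment 74%, Down-Titration 100% | 80.5% | 78.2% |
| Treatment 82%, Down-Titration 70% | 79.0% | 80.05% |
| Treatment 85%, Down-Titration 60% | 78.75% | 80.9% |
| Treatment 125%, Down-Titration 100% | 118.75% | 120.9% |
| Treatment 77%, Transition 100% | 80.3% | 79.3% |
| Down-Titration alone: weeks 1–3 75%, week 4 100% | 81.25% | 78.6% |

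Subjects can move either way across 80%, and also across 120%.

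**Width of the affected band at 80%.** Set the later period to 100% and solve for Treatment compliance.
- With Down-Titration: by days (0.80 − 0.25)/0.75 = 73.3%; by tablets (0.80 × 602 − 98)/504 = 76.1%.
- With Transition: by days (0.80 × 98 − 14)/84 = 76.7%; by tablets (0.80 × 560 − 56)/504 = 77.8%.

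Treatment compliance from the lower value to just under the upper one is classed as at least 80% overall by the rule but below 80% by the definition.

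**Early discontinuers.** Protocol 7.2 sends them through Down-Titration, so the low-tablet share is larger.
- Stop at day 42, with 70% then 100%: A = 0.70 × 42/70 + 28/70 = 82.0%. B = (0.70 × 252 + 98)/350 = 274.4/350 = 78.4%.
- Stop at day 28, with 100% Down-Titration compliance: the band runs from (0.80 × 56 − 28)/28 = 60.0% to (0.80 × 266 − 98)/168 = 68.3%.

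**The case against.** The case for leaving this alone has four parts.

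*Poor Treatment Period compliance is not hidden.* A reader might infer that good Down-Titration compliance conceals poor compliance in the period that carries the primary endpoint. The documents do not support that. Treatment compliance has its own formula at a constant 6 tablets a day, where rule and definition agree, and it is summarised and listed separately. The 75% subject above is still reported as below 80% for that period. This stands in full and limits the point to the overall and Down-Titration figures.

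*The use is descriptive.* A reader might also infer an effect on the PPS or the primary analysis. None is shown. Section 7 plans summaries and a listing only. The criteria for important protocol deviations, which determine PPS membership, are in a separate document (SAP 3.4) that was not available, so an effect there can be neither asserted nor excluded. Protocol 7.7 links persistent noncompliance to a possible withdrawal decision during the trial, but nothing says that decision uses the SAP's weighted sum. This also stands.

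*The rule is explicit and reproducible.* It is, and no stated number is wrong. The defect is that a general definition and its special-case formula give different answers.

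*Tablets are not dosage.* The protocol's limits refer to prescribed dosage, and the regimen is padded with placebo tablets. In the 50 mg/day group the Transition dose is unchanged while tablets drop from 6 to 4 a day, so there day weights follow dosage and tablet weights do not. That is correct for this one case. It does not extend to the 200 mg/day group or to Down-Titration, and it does not justify day weights under a definition that counts tablets.

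**Conclusion.** The inconsistency is real and minor. As written, the overall and Down-Titration compliance figures do not equal the section 7 definition unless compliance is the same in every duration. In the full-length examples the difference is about 1 to 3 points; for the day-42 discontinuer it is 82.0 − 78.4 = 3.6 points.

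It would go too far to say that subjects are misclassified. Reclassification needs unequal compliance between durations and a value close to 80% or 120%. The bands for full-length subjects are narrow: 73.3% to 76.1% with Down-Titration and 76.7% to 77.8% with Transition, each assuming 100% compliance in the later period. What can be said is that some subjects may be placed in the wrong class in these two summaries. How many cannot be known, because the documents contain no compliance data.

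The calculation assumes nominal period lengths and the tablet numbers in SAP 3.9.6.

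**What to change.** In SAP section 7, set W_i = (tablets due in i) / (total tablets due). Equivalently, drop the weighted sum and compute overall and Down-Titration compliance as total tablets taken divided by total tablets due. Apply the same change to the combined Treatment plus Transition or Down-Titration figure.

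The cost is one formula and the matching line of code. The formulas for Treatment and Transition alone do not change.

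There may be a practical gain. The schedule in Protocol Table 5–1 has IMP dispensed at Visit 7 and returned at Visit 8, with no visit between. The present rule needs separate returned counts for Down-Titration weeks 1 to 3 and week 4. The documents do not describe weekly packs, so that split may not be available from visit counts. A ratio of totals does not need it.

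If day weighting was intended, the SAP should instead say so, give the reason, and label the result as a time-weighted mean rather than as the defined compliance.

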# 6.3.1 Potential drug-induced liver injury IMP discontinuation criteria

Subjects with potential drug-induced liver injury (PDILI) must be assessed to determine if IMP must be discontinued. In addition, all concomitant medications and herbal supplements that are not medically necessary should also be discontinued.

The PDILI criteria below require immediate and permanent discontinuation of IMP:

- Subjects with either of the following:
  - ALT or AST  $\geq$ 5xULN
  - ALT or AST  $\geq$ 3xULN and coexisting total bilirubin  $\geq$ 2xULN

The PDILI criterion below requires immediate discontinuation of IMP:

• Subjects with ALT or AST ≥3xULN who exhibit temporally associated symptoms of hepatitis or hypersensitivity. Hepatitis symptoms include fatigue, nausea, vomiting, right upper quadrant pain or tenderness. Hypersensitivity symptoms include fever (without clear alternative cause), rash, or eosinophilia (ie, >5%).

The PDILI criterion below allows for subjects to continue on IMP at the discretion of the Investigator.

• Subjects with ALT or AST ≥3xULN (and ≥2x Baseline) and <5xULN, total bilirubin <2xULN, and no eosinophilia (ie, ≤5%), with no fever, rash, or symptoms of hepatitis (eg, fatigue, nausea, vomiting, right upper quadrant pain or tenderness).

Evaluation of PDILI must be initiated as described in Section 11.2.1. If subjects are unable to comply with the applicable monitoring schedule, IMP must be discontinued immediately.

Investigators should attempt to obtain information on subjects in the case of IMP discontinuation to complete the final evaluation. Subjects with PDILI should not be withdrawn from the study until investigation and monitoring are complete. All results of these evaluations and observations, as well as the reason(s) for IMP discontinuation and subject withdrawal (if applicable), must be recorded in the source documents. The eCRF must document the primary reason for IMP discontinuation.

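### The Treatment Period compliance denominator in SAP 7 counts days when IMP was stopped on instruction, so a fully adherent subject with a liver-safety stop can be reported below 80%

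*SAP*

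**What the plan says.** SAP 7 first gives a general definition, in which the denominator is the "Number of tablets that should have been taken". Protocol 7.7 uses the same idea: a compliant subject is a "subject within 80% and 120% of the prescribed dosage".

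SAP 7 then makes this operational. The "total planned tablet number during the Treatment Period will be calculated as 6 times the number of days", namely the "number of days from the first dose of IMP (Visit 3) up to the last visit in the period": the EDV for early discontinuers, Visit 7 for everyone else. The six tablets a day come from SAP 3.9.6 and Table 3.1. The first and last days count as half days. For overall compliance, which adds the Transition or Down-Titration Period, the weights W_i use a different end date: the latest of EDV, Visit 7 and Visit 8.

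Protocol 6.3.1 requires immediate IMP discontinuation in defined PDILI cases. It also says "Subjects with PDILI should not be withdrawn from the study" before investigation and monitoring are finished. Table 11-2 allows the stop to be temporary in one of these cases. It sets monitoring at least twice weekly until values normalize, stabilize or return to baseline, with no maximum length.

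SAP 7 reports compliance on the Safety Set with descriptive statistics, counts in three bands (<80%, 80% to 120%, >120%) and a subject listing.

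**The concern.** After an instructed stop no tablet is prescribed, so under the general definition none is due. The operational formula still adds six tablets for each such day. The rule therefore departs from the SAP's own definition and from Protocol 7.7. SAP 10.1, by contrast, ends exposure at the last dose.

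What is at stake is the meaning of the <80% band. It should show subjects who did not take what they were told to take. As written, it can also hold subjects who followed a safety instruction exactly, and the listing would show them as poor compliers.

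**Working it through.** **Inputs.** Six tablets per day (SAP 3.9.6, Table 3.1); denominator 6 x (EDV or Visit 7 date - Visit 3 date) (SAP 7); first and last day as half days (SAP 7); 12-week Treatment Period = 84 days; 80% threshold (Protocol 7.7, SAP 7). Two assumptions: all unused tablets are returned, because the numerator is dispensed minus returned; and g, the number of instructed off-drug days before the EDV or Visit 7, for which the documents give no value.

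**The SAP formula for a completer.** Counting doses: 3 (first evening) + 83 x 6 + 3 (last morning) = 504. The formula gives 6 x 84 = 504, so full adherence scores 100%. The rule is exact when dosing runs to the last visit.

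**Permanent instructed stop.** With all tablets taken for t days and the EDV g days later:

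compliance = 6t / [6(t+g)] = t/(t+g), which is below 80% if and only if g > t/4.

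| t (days on IMP) | g=3 | g=7 | g=14 | g=28 | smallest whole-day g giving <80% |
|---|---|---|---|---|---|
| 14 | 82.4% | 66.7% | 50.0% | 33.3% | 4 |
| 28 | 90.3% | 80.0% | 66.7% | 50.0% | 8 |
| 42 | 93.3% | 85.7% | 75.0% | 60.0% | 11 |
| 56 | 94.9% | 88.9% | 80.0% | 66.7% | 15 |

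If g=0 the figure is 100%. For a subject kept in the study to Visit 7 on day 84, any stop by day 67 gives less than 80% (67/84 = 79.8%; 68/84 = 81.0%).

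**Temporary instructed stop.** A subject who restarts and reaches Visit 7 on day 84 scores (84-g)/84. That is below 80% from g=17 (67/84 = 79.8%). This case does not depend on when an EDV is held.

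**The weighted sum does not rescue the rule.** SAP 7 lets a period be split into durations with different tablet counts, but Table 3.1 fixes six per day throughout the Treatment Period. A zero-tablet duration would also make C_i equal to 0/0.

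**After the fix.** Excluding the g days gives 6t/6t = 100% for every t and g.

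**Overall compliance.** Take a completer with 14 instructed off-drug days (t=70) and then a 14-day Transition Period. At present: (70/84) x (84/98) + 1 x (14/98) = 84/98 = 85.7%. Removing the 14 days from C_i and from both parts of W_i gives 1 x (70/84) + 1 x (14/84) = 100%, and the weights sum to 1. Ending the overall denominator at Visit 7 instead would give a fully adherent completer (84+14)/84 = 116.7% with Transition or (84+28)/84 = 133.3% with Down-Titration, so that end date must stay.

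**The case against.** The strongest reply is that hardly anyone is affected. Protocol 7.2 and the footnotes to Table 5-1 send early discontinuers through down-titration, with IMP dispensed at the EDV, so an ordinary withdrawal can dose up to the EDV and has no built-in gap. For pregnancy, Protocol 11.1.4 lists the EDV before the stop or down-titration, so no gap is established there either. That leaves PDILI stops, in a trial that excludes chronic hepatic disease and transaminases above 2xULN. This stands, and it limits the point to PDILI.

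Second, a late EDV is an inference. SAP 3.2.2 ties the EDV to discontinuing treatment, which suggests a visit close to the stop; Protocol 8.8 ties it to discontinuing the study. The documents are ambiguous, and every gap above is assumed. This also stands for permanent stops. It does not reach temporary stops, where the off-drug days count even if the subject completes to Visit 7.

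Third, a reader can see what happened from other outputs: last-dose dates and reasons for discontinuation (SAP 5.1.1), exposure (SAP 10.1) and PDILI listings (SAP 10.3.2). True, but the <80% count would still be wrong.

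A reader might infer that the compliance comparison between arms is biased. The documents do not support that. SAP 7 plans no test between arms, Protocol 2.4 describes discontinuation due to adverse events as low and similar to placebo, and SAP 4.2 reports no clear dose-response in dropout. A reader might also infer an effect on the Per-Protocol Set. The criteria for important protocol deviations are in a separate document (SAP 3.4), so this cannot be determined.

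**Conclusion.** The point holds for the Treatment Period formula. A stated rule gives a wrong value for a subject who obeyed an instructed stop, and it disagrees with the SAP's own definition and with Protocol 7.7. The error is g/(t+g) of full compliance and moves a fully adherent subject below 80% once g exceeds t/4. This rests on an assumed gap, complete tablet return and full adherence up to the stop; unreturned tablets would push the figure the other way.

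The reach is small: PDILI stops only, in a number the documents do not give but which is probably low. The effect is on the <80% count and the listing of a descriptive Safety Set output. The primary ANCOVA does not use compliance. It would go too far to say that safety withdrawals in general are misreported, or that overall compliance ends at the same date as the Treatment Period formula; SAP 7 gives it a later end date when there is a Visit 8.

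Separately, the passages applying down-titration to any early discontinuation (Protocol 7.2, Table 5-1 footnotes) and those requiring an immediate stop in some PDILI cases (Protocol 6.3.1, Table 11-2) must be reconciled. No clinical rule is proposed here.

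**What to change.** In SAP 7, add that days on which IMP was stopped on the investigator's instruction, permanently or temporarily, are excluded from the Treatment Period denominator. Identify them from the dosing log and the IMP discontinuation record, and apply the existing half-day convention at the stop and any restart. For subjects who stop without instruction, keep the EDV as the end date, so that real non-adherence still counts.

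For overall compliance, keep the latest of EDV, Visit 7 and Visit 8 as the end date. Remove only the same instructed off-drug days from the C_i day count and from both the numerator and the denominator of W_i, so that the weights still sum to 1.

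The cost is a short SAP addition, a small programming change and a blinded case review, which could be done at the planned data evaluation meeting. The review is needed because Protocol 6.3.1 requires the reason for IMP discontinuation in the eCRF, but the documents show no dedicated field for the date of an instructed stop.
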